14.2.4. SENSITIVITY ANALYSIS OF PRIMARY EFFICACY

The primary efficacy analysis will be performed after all subjects complete (or possibly complete) the treatment with the investigational product. Baseline adapted Mayo score is required. For missing primary efficacy endpoint (changes in the Adapted Mayo score at week 12), the latest post-baseline changes before week 12 will be carried forward if the Mayo score is missing. Imputed week 12 adapted mayo score with last observation carried forward (LOCF) method will be used in sensitivity analysis for FAS and mFAS subjects. The format on the summary statistics will keep the same as primary analysis. Complete case analysis without any imputation will be also summarized with same method in primary analysis for FAS mFAS subjects.

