5. ANALYSIS POPULATION

5.1. STAGE 1 POPULATION

Screened Set (Screened) in stage 1

The screened set will contain all subjects who signed informed consent for stage 1.

Document: Statistical Analysis Plan

Author: [name]

Version Number: 1.1

Version Date: 18Jan2023

Template No.: CS_TP_BS016 Revision 5

Reference: CS_WI_BS005

Effective Date: 01Apr2018

All Randomized Set (Randomized) in stage 1

The randomized set will contain all subjects who are randomized into stage 1, no matter treated or not.

Full Analysis Set (FAS) in stage 1

The full analysis population (FAS) will contain all randomized subjects who receive at least one dose of study medication or placebo in stage 1. FAS will be based on the planned drug taken.

Modified Full Analysis Set (mFAS) in stage 1

The modified full analysis population (mFAS) will contain all randomized subjects who receive at least one dose of study medication or placebo in stage 1 except subjects without week 12 adapted mayo score due to COVID-19. mFAS will be based on the planned drug taken.

Per Protocol Set (PPS) in stage 1

The per-protocol set (PPS) will contain a subset of FAS subjects who do not have major protocol deviation in stage 1.

Definition of major protocol deviation in stage 1:

1. Any Major clinical protocol deviation of Randomization Criteria
2. Any Major clinical protocol deviation of Eligibility and Entry Criteria
3. Any prohibited concomitant medication in clinical protocol deviation
4. IP compliance below 80% or over 120%
5. Have no baseline Adapted Mayo score
6. Have no Week12 Adapted Mayo score
7. Week 12 Adapted Mayo Score is out of visit window
8. Any unblinding during stage 1
9. Any other critical clinical protocol deviations in stage 1

Definition of minor protocol deviation in stage 1:

Clinical protocol deviation except major protocol deviation happened in stage 1.

Document: Statistical Analysis Plan

Author: [name]

Version Number: 1.1

Version Date: 18Jan2023

Template No.: CS_TP_BS016 Revision 5

Reference: CS_WI_BS005

Effective Date: 01Apr2018

Safety Set (SS) in stage 1

The safety set (SS) will contain all randomized subjects who receive at least one dose of study medication or placebo. SS will be based on the actual drug taken.

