14.2.2. PRIMARY ANALYSIS OF PRIMARY EFFICACY ENDPOINT

The primary efficacy analysis will be based on FAS, mFAS, and PPS.

The covariance (ANCOVA) model with baseline as covariate will be used to analyze the changes in adapted Mayo score from baseline at week 12 between the CBP-307 0.2 mg group and the placebo group stratified by whether the previous treatment with a tumor necrosis factor (TNF)- α antagonist failed (Yes or No). The superiority of the CBP-307 0.2 mg group to placebo on change in adapted Mayo score from baseline at week 12 after treatment will be tested at a significance level of 0.025 with one-sided. If the significance level is reached, then superiority of the CBP-307 0.2 mg will be statistically significant. For subjects enrolled in protocol version 5.0 or earlier in 0.1 mg group, they will be compared with placebo group with same method as 0.2mg QD group, but only results of 0.1 mg group will be presented as supportive results.

The least square mean (LSMEANS), together with the p values and the 95% confidence intervals, between 0.2 mg vs. placebo will be reported using the ANCOVA model (SAS PROC MIXED), with the stratification factor as the confounding factor in the ANCOVA model and the baseline values as covariate.

The change from baseline over time on the Adapted Mayo score will also be plotted by each treatment group for exploratory purpose.

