14.2.3. MISSING IMPUTATION FOR PRIMARY EFFICACY

Multiple Imputation

Multiple imputation has 3 distinct phases: Imputation, Analysis and Combining. During the Imputation Phase, the missing data values are filled-in to form a complete dataset. This is done 'm' times. For the Analysis Phase, each of the 'm' complete datasets are analysed by a statistical

Document: Statistical Analysis Plan

Author: [name]

Version Number: 1.1

Version Date: 18Jan2023

Template No.: CS_TP_BS016 Revision 5

Reference: CS_WI_BS005

Effective Date: 01Apr2018

model (as specified in Section 14.2.2). The Combining Phase pools the parameter estimates with their standard errors across the ‘m’ complete datasets and produces an average estimate with a standard error calculated using Rubin’s formula this allows for the uncertainty between imputations as well as the variability within each analysis.

Multiple imputation assumes that the data are missing at random (MAR). MAR assumes that the missingness does not depend on the actual missing values, but that the missing data can be completely explained by the observed data. To test the robustness of the multiple imputation strategy a tipping point analysis may be implemented.

In the case of mayo scores, a multiple imputation approach is implemented for the missing individual adapted mayo score.

Each individual mayo score is imputed and then the composite endpoint measures are created (see list of endpoints in APPENDIX 2).

There are 4 steps to this process:

1. Create a dataset with one record per subject, containing all values of each mayo score for all visits (baseline and week 12 on one record) in stage 1. These variables are included because they are correlated with the endpoint and/or missingness. The multiple imputation process creates complete datasets using PROC MI in SAS 9.4. During post-processing, the endpoints are derived in each of the complete datasets. The endpoints and analysis model in APPENDIX 2.
2. Run ‘m’ times Markov Chain Monte Carlo (MCMC) imputations to make the missing values in the dataset have a full missingness pattern. This will produce a dataset with an index variable _imputation_ and otherwise the same variables as the input dataset. It will have one record per imputation per subject.

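### Exploratory IBDQ: SAP 14.4.2 replaces an observed late week 12 score, normally with baseline, and its ANCOVA names no baseline covariate; as a minor second point, the primary endpoint's tipping-point analysis is optional

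*SAP*

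**What the plan says.** **IBDQ (exploratory).** SAP 14.4.2 applies LOCF in two situations: the week 12 score is missing, or the week 12 assessment falls outside its window. The value used is the latest record before week 12; nothing requires it to be post-baseline. Protocol Table 2 sets the visit at day 84±5. SAP 14.4.1.1 and Protocol Table 2 place the stage 1 IBDQ at baseline and at week 12 or early termination only. The ANCOVA sentence in 14.4.2 names the stratification factor and stops, whereas 14.2.2 and 14.3.3 name the stratification factor and the baseline value. Section 14.4.2 gives LOCF, on FAS, mFAS and PPS. Appendix 2 gives MCMC multiple imputation and LOCF, on FAS and mFAS.

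**Adapted Mayo score, for contrast.** An out-of-window value is not replaced. SAP 5.1 lists it only as a reason for exclusion from the PPS: "Week 12 Adapted Mayo Score is out of visit window".

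**Primary endpoint, missing data.** SAP 3.3 expects about 20% of week 12 adapted Mayo scores to be missing, and SAP 14.2.3 states that the multiple imputation assumes MAR. On testing that assumption it says: "To test the robustness of the multiple imputation strategy a tipping point analysis may be implemented". The committed alternatives in SAP 14.2.4 are LOCF ("the latest post-baseline changes before week 12 will be carried forward if the Mayo score is missing") and complete case ("Complete case analysis without any imputation will be also summarized with same method in primary analysis for FAS mFAS subjects"). Protocol 9.12 adds a model-based analysis that it does not define.

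**The concern.** A late questionnaire is still an outcome measured on treatment. Discarding it for the pre-treatment value sets that subject's change to zero, whatever the subject reported. In both arms this pulls the estimated difference toward zero. Leaving out a baseline score that is collected anyway gives up precision at no benefit. Because 14.4.2 and Appendix 2 differ, two programmers could produce different IBDQ tables and each be following the SAP.

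For the primary endpoint the issue is what the report is obliged to show. With a fifth of the outcomes expected to be missing, a reader will ask how much worse the unobserved active-arm subjects would have to be before the result changes. No committed analysis answers that in graded form.

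**Working it through.** **1. What happens to an out-of-window IBDQ.** With records only at baseline and visit 11:

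- Late score (after day 89): the latest record before week 12 is normally baseline, so change = 0. If baseline were not allowed to be carried, which 14.4.2 does not say, the subject would have no value.
- Early score (before day 79): it may itself be the latest record before week 12, and so may be kept.

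The share of the group difference that remains is 1 − late share, assuming equal late shares in both arms and late subjects with the same mean difference as the rest. At 5%, 10% and 20% late it is 0.95, 0.90 and 0.80. The documents give no out-of-window share, so the range is an assumption.

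**2. IBDQ model without baseline.** With equal SDs at baseline and week 12 and correlation ρ, the residual variance after baseline adjustment is (1+ρ)/2 of the change-score variance. The SE ratio without baseline is therefore √(2/(1+ρ)):

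- ρ = 0.6: √1.25 = 1.12
- ρ = 0.3: √1.538 = 1.24

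The correlations and equal SDs are assumptions.

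**3. The plan's sample size (Protocol 9.2, SAP 7.4).** Difference 1.2, SD 2.0, two-sided 0.05, 80% power: n = 2 × (1.960 + 0.842)² × 2.0² / 1.2² = 43.6, so 44 evaluable per arm; 44/0.85 = 51.8, so 52. This reproduces the plan's figure. At 20% missing, 52 × 0.8 = 41.6 per arm remain, or 83.2 of 104.

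**4. How different the committed primary-endpoint analyses are.**

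- The mFAS is the treated randomized set "except subjects without week 12 adapted mayo score due to COVID-19". Complete case drops those subjects anyway, so complete case on FAS and on mFAS uses the same people (about 83 of 104).
- The PPS excludes subjects who "Have no Week12 Adapted Mayo score", so it has no missing primary outcome.
- The adapted Mayo score needs endoscopy, scheduled in stage 1 only at screening and at week 12 or early termination, which share visit 11. Weeks 2, 4 and 8 give partial Mayo scores only. LOCF therefore equals complete case **if** early-termination scores count as week 12, **and** the change in total score is what is carried, **and** no unscheduled endoscopy exists. Otherwise the two can differ.

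**5. Illustration of a tipping point.** Assume an estimate of 1.2 under MAR, SD of change 2.0, 52 per arm, 20% missing in each arm, and a penalty d on all missing active-arm scores. Significance is lost at d = (1.2 − half-width)/0.20, with SE = SD × √(2/41.6) and a t-based half-width.

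| Model | Residual SD | SE | Half-width | d |
|---|---|---|---|---|
| Unadjusted | 2.000 | 0.439 | 0.873 | 1.64 |
| Adjusted, SD ratio 1.0, ρ 0.3 | 1.612 | 0.354 | 0.704 | 2.48 |
| Adjusted, SD ratio 1.0, ρ 0.6 | 1.789 | 0.392 | 0.781 | 2.10 |
| Adjusted, SD ratio 0.7, ρ 0.3 | 1.844 | 0.404 | 0.805 | 1.98 |
| Adjusted, SD ratio 0.5, ρ 0.3 | 1.957 | 0.429 | 0.854 | 1.73 |
| Adjusted, SD ratio 0.5 or 0.7, ρ 0.6 | 1.985 | 0.435 | 0.866 | 1.67 |

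The SD ratio r is baseline over week 12. Residual SD = 2.0 × √((1−ρ²)/(1+r²−2rρ)). A ratio below 1 is plausible because entry restricts the baseline score to 4–9, while week 12 can run from 0 to 9.

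**The case against.** **On the IBDQ.** The endpoint is exploratory and nothing confirmatory hangs on it. The missing covariate may be a drafting slip: the model is called ANCOVA, and two neighbouring sections include baseline. Appendix 2 lists multiple imputation, so LOCF may not be the only IBDQ analysis. All of this stands, and it limits the weight of the point. It does not make the out-of-window rule right, and the shrinkage toward zero is conditional on similar late shares in the two arms.

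**On the primary endpoint.** A reader might infer that the primary analysis is invalid, or that missing data go unexamined. The documents do not support that. Multiple imputation under MAR is an acceptable primary method. LOCF rests on an assumption other than MAR. The mFAS addresses COVID-19 absences, and Protocol 9.12 promises further model-based work. Subjects with a missing week 12 rating count as non-responders, although only for the binary endpoints. What stands is narrower: none of these is a graded departure from MAR for the primary mean difference.

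A reader might also infer that LOCF simply duplicates complete case. That too goes beyond the text. SAP 4.2 suggests that early-termination scores are visit 11 data, but the SAP does not say so for the primary endpoint. Nor does 14.2.4 settle the level of carry-forward: 14.2.3 imputes the individual Mayo components, and stool frequency and bleeding are scored at weeks 2, 4 and 8. For a subject with a week 12 endoscopy but no usable diary days, component-level LOCF would give a value where complete case has none.

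**Conclusion.** The out-of-window IBDQ rule is wrong as written: an observed late score is normally turned into zero change. With 5% to 20% of each arm late (assumed, equal shares), the group difference shrinks by 5% to 20%. The ANCOVA as written costs about 12% to 24% in standard error at assumed correlations of 0.6 to 0.3 with equal SDs. The conflict between 14.4.2 and Appendix 2 is a plain inconsistency.

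The primary-endpoint point is true but minor, mostly missing detail: the one analysis aimed at MAR is optional and has no range. In the illustration, significance is lost at a penalty of about 1.6 points unadjusted, and about 1.7 to 2.5 points with baseline adjustment, depending on the assumed correlation and SD ratio. These figures show scale only; the documents give no delta to judge them against.

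Overall severity is low, because the firm errors affect an exploratory endpoint and leave the primary test intact.

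**What to change.** **IBDQ (SAP 14.4.2 and Appendix 2).**

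- Analyse the observed week 12 score even when it is out of window, provided it was collected before the first stage 2 dose, which is where SAP section 6 ends the stage 1 analysis period. Add a check restricted to in-window scores.
- Add baseline IBDQ as a covariate.
- Use the multiple imputation already listed in Appendix 2 for scores that are truly missing.
- Make 14.4.2 and Appendix 2 agree on method and populations.

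**Primary endpoint (SAP 14.2.3 and 14.2.4).**

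- Commit to a delta-adjusted tipping-point multiple imputation on the FAS, with the delta range stated in advance. If stage 1 has already been unblinded, label it post hoc.
- State one rule for whether early-termination scores count as week 12, applied to multiple imputation, LOCF and complete case alike. State also whether LOCF carries the total change or the components.

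**Cost.** SAP wording and modest extra programming; no new data. Keeping out-of-window IBDQ scores adds some variation in assessment timing, which the in-window check makes visible.

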14.3. SECONDARY EFFICACY

The secondary efficacy analyses will be performed in the FAS, mFAS, and PPS. The same analyses as primary endpoints will be performed on the secondary quantitative efficacy endpoints.

14.3.1. SECONDARY ANALYSES ON EFFICACY ENDPOINTS

- Change in adapted Mayo score at week 12 from baseline: 0.1 mg vs placebo (only 0.1 mg group presented)
- Change in complete Mayo score at week 12 from baseline: 0.2 mg vs placebo
- Change in complete Mayo score at week 12 from baseline: 0.1 mg vs placebo (only 0.1 mg group presented)
- Clinical response rate by Adapted Mayo Score at week 12: 0.2 mg vs placebo (defined as a decrease of ≥ 2 points and at least 30% from baseline, accompanied with a decrease of ≥ 1 point from baseline in the rectal bleeding subscore or an absolute rectal bleeding

Document: Statistical Analysis Plan

Author: [name]

Version Number: 1.1

Version Date: 18Jan2023

Template No.: CS_TP_BS016 Revision 5

Reference: CS_WI_BS005

Effective Date: 01Apr2018

subscore of <= 1 point)

- Clinical response rate by Adapted Mayo Score at week 12: 0.1 mg vs placebo
- Clinical response rate by Complete Mayo Score at week 12: 0.2 mg vs placebo (defined as a decrease of >= 3 points and at least 30% from baseline, accompanied with a decrease of >= 1 point from baseline in the rectal bleeding subscore or an absolute rectal bleeding subscore of <= 1 point)
- Clinical response rate by Complete Mayo Score at week 12: 0.1 mg vs placebo
- Clinical remission rate by Adapted Mayo score at week 12: 0.2 mg vs placebo (defined as a rectal bleeding subscore = 0 and stool frequency sub score <= 1, with an Endoscopy subscore <=1 [excluding friability])
- Clinical remission rate by Adapted Mayo score at week 12: 0.1 mg vs placebo
- Clinical remission rate by Complete Mayo score at week 12: 0.2 mg vs placebo (defined as a total Mayo score of <= 2 points with no individual subscore > 1 point)
- Clinical remission rate by Complete Mayo score at week 12: 0.1 mg vs placebo
- Mucosal healing rate at week 12: 0.2 mg vs placebo (defined as Mayo endoscopic subscore <= 1)
- Mucosal healing rate at week 12: 0.1 mg vs placebo

14.3.2. MISSING DATA METHODS FOR SECONDARY EFFICACY

VARIABLES

For the quantitative efficacy endpoint (changes in the Mayo score at week 12), the MI, LOCF, and complete case analysis will be presented if the Mayo score is missing in FAS and mFAS population.

For the qualitative efficacy analyses, subjects with any missing individual rating at week 12 will be considered as non-responders.

Endoscopy video will be obtained during each endoscopy and will be sent to Bioclinica for

Document: Statistical Analysis Plan

Author: [name]

Version Number: 1.1

Version Date: 18Jan2023

Template No.: CS_TP_BS016 Revision 5

Reference: CS_WI_BS005

Effective Date: 01Apr2018

central reading and determination of the Mayo endoscopy score. The result of the central reading of the endoscopy will be used to ensure subject eligibility prior to randomization and to calculate the Mayo score at analysis time points specified in the SAP. The Mayo score used for clinical endpoints in the study will utilize the Mayo endoscopy score derived from the central reader. The Mayo endoscopic score read by the investigator will be used as the Mayo score for clinical endpoints in case central reading endoscope data is missing.

14.3.3. ANALYSIS OF SECONDARY EFFICACY VARIABLES

Unless otherwise specified, all secondary efficacy analyses will be performed between treatment group and placebo and based on FAS and PPS. All results of these comparative analyses are used for exploratory purpose.

The clinical response rate at week 12, clinical remission rate at week 12, and mucosal healing rate at week 12 will be analysed

Summary statistics of qualitative statistic will be provided by each treatment group. Statistical comparison between the 0.2 mg CBP-307 group versus the placebo group and between 0.1 mg versus placebo group will be conducted using the Cochran Mantel Haenszel (CMH) test, stratified by whether treatment with a tumor necrosis factor (TNF)- α antagonist failed (Yes or No). The p-value on the rate difference and the 95% Newcombe confidence interval (CI) will be provided.

For example:

The null hypothesis to be tested is that the clinical response rate at week 12 is not different between the 0.2 mg treatment group and the placebo treatment group; i.e.,

$$H_0: \text{clinical response rate at week 12}_{0.2 \text{ mg}} = \text{clinical response rate at week 12}_{\text{placebo}}$$

The alternative hypothesis is that clinical response rate at week 12 in the 0.2 mg treatment group is higher than that of the placebo treatment group, i.e.,

$$H_A: \text{clinical response rate at week 12}_{0.2 \text{ mg}} \neq \text{clinical response rate at week 12}_{\text{placebo}}$$

Document: Statistical Analysis Plan

Author: [name]

Version Number: 1.1

Version Date: 18Jan2023

Template No.: CS_TP_BS016 Revision 5

Reference: CS_WI_BS005

Effective Date: 01Apr2018

for quantitative summary statistics, the least square mean (LSMEANS), together with the p values and the 95% confidence intervals, between 0.2 mg vs. placebo and between 0.1 mg vs. placebo will be reported using the ANCOVA model (SAS PROC MIXED), with the stratification factor as the confounding factor in the ANCOVA model and the baseline values as covariate.

14.4. EXPLORATORY EFFICACY

14.4.1. EXPLORATORY EFFICACY VARIABLE & DERIVATIONS

14.4.1.1 IBDQ Score

The Inflammatory Bowel Disease Questionnaire (IBDQ) (see Appendix 1 in protocol) is a psychometrically validated subject self-assessment scale used to measure the disease-specific quality of life in subjects with inflammatory bowel diseases including UC. IBDQ contains 32 items related to four aspects: intestinal function, emotional status, systemic symptoms, and social ability. The four aspects are scored as follows:

- Intestinal symptoms (10-70): question 1, 5, 9, 13, 17, 20, 22, 24, 26, 29
- Systemic symptoms (5-35): question 2, 6, 10, 14, 18
- Emotional function (12-84): question 3, 7, 11, 15, 19, 21, 23, 25, 27, 30, 31, 32
- Social ability (5-35): question 4, 8, 12, 16, 28

For each aspect, the higher the score is, the better the quality of life is. IBDQ is used as an endpoint indicator of the study and will be completed by the subjects themselves at baseline and at week 12 (or early termination visit).

The exploratory efficacy variable regarding to IBDQ is:

- Change from baseline at week 12 (stage 1) in IBDQ total and subscale scores (Bowel Systems, Emotion Health, Systemic Systems, and Social Function): 0.2 mg vs placebo
- Change from baseline at week 12 (stage 1) in IBDQ total and subscale scores: 0.1 mg vs

Document: Statistical Analysis Plan

Author: [name]

Version Number: 1.1

Version Date: 18Jan2023

Template No.: CS_TP_BS016 Revision 5

Reference: CS_WI_BS005

Effective Date: 01Apr2018

placebo

- Change from baseline at week 24 (stage 2) in IBDQ total and subscale scores: 0.2 mg vs placebo
- Change from baseline at week 24 (stage 2) in IBDQ total and subscale scores: 0.1 mg vs placebo
- Change from baseline at week 48 (stage 2) in IBDQ total and subscale scores: 0.2 mg vs placebo
- Change from baseline at week 48 (stage 2) in IBDQ total and subscale scores: 0.1 mg vs placebo

Other efficacy endpoints in stage 1

- Exploratory clinical remission rate at week 12 by adapted Mayo score: 0.2 mg vs placebo (defined as a rectal bleeding subscore ≤ 1 and a stool frequency subscore ≤ 1 , with an Endoscopy subscore ≤ 1 [excluding friability]).
- Exploratory clinical remission rate at week 12 by adapted Mayo score: 0.1 mg vs placebo

Efficacy endpoint in stage 2 sub-study 1

- Percentage of subjects who maintain clinical response at week 48: 0.2 mg vs placebo
- Percentage of subjects who maintain clinical response at week 48: 0.1 mg vs placebo
- Percentage of subjects who achieve clinical remission at week 48: 0.2 mg vs placebo
- Percentage of subjects who achieve clinical remission at week 48: 0.1 mg vs placebo
- Percentage of subjects who achieve mucosal healing under endoscope at week 48: 0.2 mg vs placebo
- Percentage of subjects who achieve mucosal healing under endoscope at week 48: 0.1 mg vs placebo

Document: Statistical Analysis Plan

Author: [name]

Version Number: 1.1

Version Date: 18Jan2023

Template No.: CS_TP_BS016 Revision 5

Reference: CS_WI_BS005

Effective Date: 01Apr2018

- Percentage of subjects who take oral corticosteroids at baseline, has discontinued treatment with corticosteroids at week 48 and achieved clinical remission: 0.2 mg vs placebo
- Percentage of subjects who take oral corticosteroids at baseline, has discontinued treatment with corticosteroids at week 48 and achieved clinical remission: 0.1 mg vs placebo
- Change in the complete Mayo score at week 48 from baseline: 0.2 mg vs placebo
- Change in the complete Mayo score at week 48 from baseline: 0.1 mg vs placebo
- Change in the adapted Mayo score at week 48 from baseline: 0.2 mg vs placebo
- Change in the adapted Mayo score at week 48 from baseline: 0.1 mg vs placebo
- Percentage of Subjects Who Take Oral Corticosteroids at Baseline, Has Discontinued Treatment with Corticosteroids at Week 48 and Achieved Clinical Remission

Efficacy endpoint in stage 2 sub-study 2

- Percentage of subjects who achieve clinical response at week 24 (at week 12 after treatment in sub-study 2)
- Percentage of subjects who achieve clinical remission at week 24 (at week 12 after treatment in sub-study 2)
- Percentage of subjects who achieve mucosal healing under endoscope at week 24 (at week 12 after treatment in sub-study 2)
- Change in the adapted Mayo score at week 24 (at week 12 after treatment in sub-study 2) from week 12
- Change in the complete Mayo score at week 24 (at week 12 after treatment in sub-study 2) from week 12
- Percentage of subjects who maintain clinical response at week 48 (at week 36 after treatment in sub-study 2) (i.e., have clinical response at both week 24 and week 48)

Document: Statistical Analysis Plan

Author: [name]

Version Number: 1.1

Version Date: 18Jan2023

Template No.: CS_TP_BS016 Revision 5

Reference: CS_WI_BS005

Effective Date: 01Apr2018

- Percentage of subjects who achieve clinical remission at week 48 (at week 36 after treatment in sub-study 2)
- Percentage of subjects who achieve mucosal healing under endoscope at week 48 (at week 36 after treatment in sub-study 2)
- Change in the complete Mayo score at week 48 (at week 36 of treatment in sub-study 2) from week 12:
- Change in the adapted Mayo score at week 48 (at week 36 after treatment in sub-study 2) from week 12
- Percentage of Subjects Who Take Oral Corticosteroids at Baseline, Has Discontinued Treatment with Corticosteroids at Week 48 and Achieved Clinical Remission

Efficacy endpoint in all stages for 0.2mg only:

- Change in the adapted Mayo score from baseline
- Change in the complete Mayo score from baseline
- Percentage of subjects who achieve clinical response at week 12 and week 48
- Percentage of subjects who achieve clinical remission at week 12 and week 48
- Percentage of subjects who achieve mucosal healing under endoscope at week 12 and week 48

Change from Baseline by Visit in IBDQ Total and Subscale Scores by VisitSummary of Percentage of Subjects Who Take Oral Corticosteroids at Baseline, Has Discontinued Treatment with Corticosteroids at Week 48 and Achieved Clinical Remission

